VERSION DATE: May 4, 2018

Analysis of Aim 1: ADAPT comparative effectiveness hypotheses will be tested using standard normal theory Analysis of Variance and multiple regression techniques in structural equation modeling (SEM) with a focus on growth curve analyses for follow up data. We will specify analyses to test Hypothesis 1: NGR families in both the ADAPT group-based condition and the ADAPT web-facilitated condition will show greater pre-post improvements in observed parenting, and parent, child, and couple functioning relative to the self-directed web condition; and Hypothesis 2: ADAPT group-based condition will be equally effective as the individualized ADAPT web-facilitated condition.

Analyses for Hypothesis 1 of Aim 1. We will employ standard normal theory pre-post Analysis of Variance and structural equation modeling (SEM) growth curve analyses for the long-term follow up. For the immediate pre-post analyses we will conduct a 3 group by 2 repeated measures Analysis of Variance for parenting, child, and couple functioning constructs focusing on the comparison of change across the Group Based, Individualized Facilitated, and Self-directed ADAPT conditions. The study randomly allocates 360 NGR families across the three conditions ($n = 120$ per group). For the 6-month assessment, we estimate a projected 5% attrition rate and over the 24-month follow up we expect roughly 15% attrition. In two prior PMTO randomized trials with intensive multiple-method family assessments, family retention was 88% and 86%, respectively, at 30-month follow-ups [2, 12]. In both of those studies, there were no differential rates of attrition between intervention and controls, there was less than 5% attrition by the immediate 6 month post-test assessment, and less than 15% attrition by the 24 month assessment. Using an alpha level of .05 and considering 5% attrition over the first 6 months, a pre-post design with 3 groups of 114, within subject $SD = 1$, and between groups $SD = .71$; the study is powered .81 to minimally detect a small group by time interaction effect ($ES = .12$), small time effect ($ES = .15$), and small group effect ($ES = .21$) for given parenting, child, couple or parent constructs.

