identify the model that best characterizes patterns of growth. We can also specify an additional nonlinear quadratic factor, a higher order polynomial function to capture any nonlinearity. Accelerated or decelerated change would be specified with loadings fixed at 0, 1, 4, and 16. A sequential set of models tests the latent variances and model fit across a random intercept, linear growth, and quadratic model to determine the optimal growth pattern. The comparative effectiveness hypothesis for observed parenting is shown in Figure 2 as linear growth. Group Based and Web Facilitated will be contrasted to the Self-Directed omitted group. Analyses will test that the Group Based effect ($\beta_1 > 0$) and the Web Facilitated ($\beta_2 > 0$) will show greater 2-year improvements relative to Self-Directed. For the LGM in Figure 2 we estimated power using Mplus Monte Carlo simulations with 1000 replications. An advantage of this approach is the ability to incorporate specific patterns of expected attrition over time. For the figure in Figure 3, contrasts for Group Based and Web Facilitated were fixed at a mean of .33 and variance of .22 representing the random allocation across groups. The latent initial status intercept and latent growth factors were specified reflecting a commonly observed ratio of 5:1 for the variance components (Initial Status $\psi_2 = .5$ and SD = .70; and Linear Growth $\psi_2 = .1$, SD = .31). The effect size (ES) is then the ratio of group contrast mean differences in the latent growth factor divided by the SD for growth. A sample size of 306 (cumulative attrition of 15% over 2 years, specified as .05, .10 and .15 over time) obtained power of .98 respectively to detect small effects (ES=.10) for β_1 and β_2 relative to Self-Directed and likewise for child, couple, parent adjustment.

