Analyses for Hypothesis 2 of Aim 1. To test whether the ADAPT Group Based and Web Facilitated have similar effects we will employ two related approaches to test whether ($\beta_1 = \beta_2$) for the paths shown in Figure 2. First, using the same model specification shown in Figure 2, we will further specify equality constraints in the LGM model to directly compare the relative magnitude of β_1 and β_2 . Second, we will conduct a one-sided non-inferiority test (i.e., a test of equivalence) for the intent to treat growth slope factor means and variances for the respective parenting, child, couple, and parent adjustment constructs; hypothesizing no differences between the Group Based and Web Facilitated conditions. We used the non-inferiority module in the Power Analysis and Sample Size program for the equivalence test of means using two one-sided tests for two groups of 102 (Group Based and Web Facilitated). The study is powered .82 using a .05 one-sided alpha when the reference mean = 1 and the comparison mean = 1, and the range of difference still results in the conclusion of equal means when the comparison group is plus or minus a quarter of a standard deviation of the reference mean ($\pm .25$ SDs). Finally, we will also examine dosage, participation, and variation in fidelity as potential moderators of group intervention effects.

PROTOCOL TITLE: Comparing Web, Group, and Telehealth Formats of a Military

Parenting Program

VERSION DATE: May 4, 2018

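### The growth-model power of .98 at ES = .10 does not follow from the protocol's own effect-size definition; with 306 families it is about .11 two-sided (.18 one-sided)

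*Protocol*

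**What the plan says.** The power statement is in Protocol section 1.1, in the follow-up analyses for Hypothesis 1 of Aim 1. It comes from a Mplus Monte Carlo study with 1000 replications of a linear growth model with time scores 0, 1, 2 and 4. The inputs given in the text are:

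- **Contrasts:** "contrasts for Group Based and Web Facilitated were fixed at a mean of .33 and variance of .22 representing the random allocation across groups".
- **Variances:** a "commonly observed ratio of 5:1 for the variance components", namely .5 for initial status (SD .70) and .1 for linear growth (SD .31).
- **Effect size:** "The effect size (ES) is then the ratio of group contrast mean differences in the latent growth factor divided by the SD for growth".
- **Sample:** "A sample size of 306 (cumulative attrition of 15% over 2 years, specified as .05, .10 and .15 over time").

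The result is that this sample "obtained power of .98 respectively to detect small effects (ES=.10") for each of β1 and β2 relative to Self-Directed, and "likewise for child, couple, parent adjustment". The directional hypotheses are β1 > 0 and β2 > 0.

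For this simulation the text gives no residual variance, intercept-slope covariance, alpha or sidedness. Some of these may be in Figures 2 and 3, which are not reproduced in the copy available. Section 17.2 repeats the pre-post ANOVA power but not the .98.

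**The concern.** The effect size is a standardised difference between two arm means on the growth factor. A difference of a tenth of an SD between two groups of about 100 is known to be hard to detect, so a power of .98 is implausible at sight. Modelling growth as a latent variable does not help, because a model that must estimate slopes from noisy repeated measures cannot do better than one that observes them exactly.

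This is the protocol's only power figure for the long-term contrasts against Self-Directed, and it is carried over to the child, couple and parent outcomes. A reader who trusts it would take a non-significant growth contrast as strong evidence against even a very small difference. Under the printed definition such a difference would be missed in more than eight of ten trials.

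**Working it through.** **Inputs.** Growth variance .1, the ES definition and N = 306 are from section 1.1. The arm size of 102 is 306/3 and agrees with the equivalence calculation in the same section ("two one-sided tests for two groups of 102 (Group Based and Web Facilitated")). At randomisation there are 360/3 = 120 per arm ("The study randomly allocates 360 NGR families across the three conditions"). Alpha .05 is stated for the pre-post ANOVA and is assumed to carry over. Sidedness is not stated, so both are shown.

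**1. Attempt to reproduce .98, best case (slopes observed without error).**

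- Slope difference at ES = .10: .10 × √.1 = .0316.
- SE = √(.1 × 2/102) = .0443.
- z = .0316/.0443 = .714.
- Two-sided power = Φ(.714 − 1.960) + Φ(−.714 − 1.960) = .110.
- One-sided power = Φ(.714 − 1.645) = .176.

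With all 120 per arm complete, SE = .0408 and z = .775, giving .121 two-sided and .192 one-sided. The stated figure is not reproduced.

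**2. What .98 would require.** The ES needed is (z for alpha + z for power) × √(2/n). At n = 102:

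| Power | Two-sided ES | One-sided ES |
|---|---|---|
| .80 | (1.960 + .842) × .140 = .392 | (1.645 + .842) × .140 = .348 |
| .98 | (1.960 + 2.054) × .140 = .562 | (1.645 + 2.054) × .140 = .518 |

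At ES = .10, power .98 needs 2 × ((1.960 + 2.054)/.10)² ≈ 3,222 families per arm two-sided, or 2,736 one-sided.

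**3. The growth model itself.** This step uses the maximum likelihood information matrix with waves at 0, 1, 2 and 4, 120 per arm, cumulative dropout .05/.10/.15, variances .5 and .1, uncorrelated intercept and slope, and free baseline arm means. The residual variance is not given, so a range is assumed:

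| Assumed residual variance | Power at ES = .10, two-sided | ES for power .80, two-sided |
|---|---|---|
| 0 | .117 | .371 |
| .1 | .108 | .401 |
| .25 | .099 | .435 |
| .5 | .089 | .482 |
| 1.0 | .079 | .564 |

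**4. Contrasts simulated as uncorrelated covariates of variance .22.** True arm indicators are negatively correlated, but the stated input could have been entered without that correlation. Then z = .10 × √(306 × .22) = .820, which gives .130 two-sided and .205 one-sided. With 360 families z = .890, which gives .144 and .225.

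**5. Intercept-slope correlation.** With equal baselines and no residual error, a correlation r multiplies z by 1/√(1 − r²). Reaching two-sided .98 at 102 per arm needs r = √(1 − (.10/.562)²) = .984. Over 102 or 120 per arm, correlated or uncorrelated contrasts and both sidedness choices, the value needed is .970 to .984. At r = ±.8, power is .22 to .32 two-sided and .33 to .44 one-sided.

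**The case against.** The strongest counter-argument is that .98 may be a genuine simulation output whose effect size was mislabelled. Two readings were tried.

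- **.10 as the raw slope path.** This is an ES of .10/√.1 = .32. With 102 per arm it gives z = .10/.0443 = 2.26 and power .62 two-sided (.73 one-sided). With uncorrelated contrasts of variance .22 it gives .74 (.83), and with 360 families .80 (.88). That is far above .11, but it is not .98.
- **.10 as the share of growth variance explained jointly by two uncorrelated contrasts.** Each contrast explains .005 = β² × .22, so β = .151, an ES of about .48. With residual growth variance .09, z = .151 × √(306 × .22/.09) ≈ 4.12 and power is .985 two-sided. This matches, but only with no residual error and uncorrelated contrasts.

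Both readings contradict the printed definition, and the second is conjecture. They do show that the wrong item may be the ES label and not the power. What stands is that the figure of .11 is conditional: it applies if the definition and ES = .10 are both kept.

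It is also true that the simulation input is not visible and that alpha and sidedness are assumed. This limits what can be said about the cause. It does not restore agreement within the paragraph, because error-free slopes are the favourable limit unless intercept and slope are almost perfectly correlated.

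Finally, the impact is limited. Section 17.2 omits the .98, and nothing links the 360 families to it.

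**Conclusion.** The concern holds. The ES definition, the ES value and the power in the growth-model paragraph cannot all be right. Under the printed definition, power at ES = .10 is .11 two-sided or .18 one-sided with 102 per arm and error-free slopes. It is .08 to .12 two-sided in the growth model over assumed residual variances of 0 to 1.0. The stated .98 belongs to an ES of about .56 (.52 one-sided), more than five times the value printed.

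This rests on alpha .05, equal allocation, the stated growth variance, and no near-perfect intercept-slope correlation. The document does not reveal which of the three items is wrong. The finding concerns the sensitivity claimed for the long-term contrasts. It is not a finding that the sample size or the planned model is wrong. It should be fixed.

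**What to change.** Check the effect and variance inputs of the Monte Carlo study, then reconcile the ES definition, the ES value and the power in section 1.1. State the alpha, sidedness, residual variance and intercept-slope covariance used.

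- **If the definition and ES = .10 stand,** replace .98. Possible wording: *With 306 families, power for each growth contrast against Self-Directed at ES = .10 is about .11 two-sided (.18 one-sided) with error-free slopes; power .80 needs an ES of about .39 two-sided (.35 one-sided), and more with residual error.*
- **If the simulated effect was larger,** keep .98 and restate the ES, in growth-SD units, at the value actually simulated.
- **If ES was meant on another scale,** correct the definition sentence and give the equivalent in growth-SD units.

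Make the same correction where the claim is extended to child, couple and parent adjustment.

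The cost is a look at one input file and one or two reworded sentences. No families are added and the analysis does not change. The stated sensitivity will look less favourable if the first or second case applies.

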1.0 Objectives

1.1 Purpose:

The overarching goal of this study is to advance research on family-based prevention of negative child outcomes for reintegrating Operation Enduring Freedom/Operation Iraqi Freedom personnel by evaluating different formats of a parenting program, After Deployment, Adaptive Parenting Tools/ADAPT. The ADAPT program is based upon the Parent Management Training-Oregon Model/PMTO, but adapted for military deployed families. We will examine which of three delivery formats of ADAPT is most effective at reducing youth risk behaviors associated with negative childhood outcomes by improving parenting, child, and parent adjustment. There is a clear intent to benefit all subjects in this study (except surveyed teachers), including children.

We will conduct a three-group, two-site randomized trial to test the comparative effectiveness of ADAPT delivery approaches. The study will randomly allocate 360 NGR families to one of three conditions: (i) group-based web-enhanced ADAPT; (ii) individualized web-facilitated ADAPT; or (iii) self-directed web ADAPT.

Thus, specific aims are as follows:

1. Conduct a three-group, two-site randomized trial to test the comparative effectiveness of ADAPT delivery approaches
 - a. Families will complete a pre-intervention baseline assessment and post-intervention follow-up assessments at 6, 12- and 24 months.
2. Test the generalizability of ADAPT effectiveness across three delivery approaches using intent to treat (ITT) analyses
 - a. Test the value-added impact of group-based delivery relative to facilitated and self-directed web approaches
 - b. Comparative effectiveness will be tested by specifying a non-equivalence hypothesis for group based and individualized facilitated relative to self-directed web only

We hypothesize that (1) individualized web-facilitated parenting intervention will be equally effective as the group-based web-enhanced intervention, and (2) both individualized and group-based ADAPT will be more effective than a self-directed web-condition. Effective internet delivery methods will facilitate development of new approaches to engage military families separated by deployment, isolated by geographical location, and in need of strategies to deal with deployment and reintegration stressors, directly addressing limitations and barriers to access to evidence based prevention programs.

PROTOCOL TITLE: Comparing Web, Group, and Telehealth Formats of a Military Parenting Program

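### Hypothesis 2 (group and telehealth delivery equally effective) is given two unranked tests, and one of them, the β1 = β2 equality constraint, cannot support it

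*Protocol*

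**What the plan says.** Protocol section 1.1 (Analysis of Aim 1) words Hypothesis 2 as follows: "ADAPT group-based condition will be equally effective as the individualized ADAPT web-facilitated condition". The paragraph on analyses for Hypothesis 2 says that, to examine whether the two formats "have similar effects we will employ two related approaches to test whether" β1 equals β2. Here β1 and β2 are the Group Based and Web Facilitated effects on the growth factor, each relative to Self-Directed.

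- **First approach:** "we will further specify equality constraints in the LGM model to directly compare the relative magnitude of" β1 and β2.
- **Second approach:** "Second, we will conduct a one-sided non-inferiority test (i.e., a test of equivalence) for the intent to treat growth slope factor means and variances", with a margin of ±.25 SD.

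The only power statement for Hypothesis 2 belongs to the second approach. It describes an "equivalence test of means using two one-sided tests for two groups of 102 (Group Based and Web Facilitated") and continues: "The study is powered .82 using a .05 one-sided alpha when the reference mean = 1 and the comparison mean = 1".

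The paragraph does not rank the approaches, does not say how a non-significant constraint will be read, and does not say what follows if the two disagree. Section 17.1 (Data Analysis Plan) repeats the analysis of variance and the growth model but does not return to Hypothesis 2.

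**The concern.** Constraining β1 = β2 and examining the loss of fit is a test of difference. Its null hypothesis is the very statement that Hypothesis 2 wants to establish. Retaining that null becomes more likely as the sample shrinks, attrition rises or the outcome gets noisier. A valid route to a claim of similarity works the other way: it takes a difference of at least the margin as the null and becomes harder to pass as precision falls.

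Because the constraint is listed first and on a par with the equivalence test, a report could satisfy the text by citing a non-significant constraint when the margin-based test has failed. The conclusion at stake is the trial's main message on telehealth: that it can stand in for group delivery.

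**Working it through.** **Inputs from the protocol (section 1.1).** 102 families per arm after 15% attrition; 120 per arm randomised; margin ±.25 SD; one-sided alpha .05 and stated power .82 for the equivalence test; latent slope variance .1; growth loadings 0, 1, 2, 4.

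**Assumptions.** The protocol sets no level for the constraint test, so I take a two-sided .05 test with 1 degree of freedom. It gives no residual variance, so I show a range.

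**1. The plan's own figure.** SE = √(2/102) = .140 SD, and .25/.140 = 1.785.

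- Two one-sided tests, true difference 0: 2Φ(1.785 − 1.645) − 1 = .112.
- One-sided non-inferiority, true difference 0: Φ(1.785 − 1.645) = .556.

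The stated .82 is not reproduced by either. It is approached only on readings that the text does not give: one-sided non-inferiority with a raw margin of .25 and SD .70 (.817), or with 204 per arm (.811). Two one-sided tests would need 286 per arm, or a margin of about .42 SD.

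**2. The constraint when the true difference equals the margin.** Power = Φ(.25/SE − 1.96), the opposite tail being negligible.

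| Per arm | SE (SD units) | Power | Non-significant |
|---|---|---|---|
| 102 | .140 | .431 | 56.9% |
| 114 | .132 | .471 | 52.9% |
| 120 | .129 | .491 | 50.9% |

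For 80% power to reject the constraint at .25 SD, 252 per arm would be needed.

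**3. The same on the growth-model scale.** With occasions at 0, 1, 2, 4 the sum of squares about the mean is 21 − 4(1.75)² = 8.75. The variance of one family's estimated slope is therefore .1 + σ²/8.75, where σ² is the residual variance. The margin is .25 × √.1 = .079, and SE = √(2 × variance/102).

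| Assumed σ² | Slope variance | SE | Non-significant |
|---|---|---|---|
| 0 | .100 | .044 | 57% |
| .25 | .129 | .050 | 65% |
| .5 | .157 | .056 | 70% |
| 1.0 | .214 | .065 | 77% |

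**4. How often the two approaches disagree (102 per arm, SE .140).** The constraint is non-significant when the estimate lies within ±1.96 × .140 = ±.274. The two one-sided tests succeed only when it lies within ±(.25 − 1.645 × .140) = ±.020.

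- True difference 0, two one-sided tests: the constraint is non-significant in 95% of trials and equivalence is shown in 11%, so they part company in about 84%.
- True difference 0, one-sided non-inferiority: the constraint is non-significant while non-inferiority fails in Φ(−.140) − Φ(−1.96) = .444 − .025, about 42%.
- Telehealth truly worse by .25 SD, one-sided non-inferiority: the constraint is non-significant while non-inferiority fails in Φ(1.645) − Φ(−.175) = .950 − .431, about 52%.

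**5. A reading that weakens the result.** If the margin were .25 raw units with SD .70, SE = .098 and the constraint would be non-significant in 27.7% of trials. If .25 were raw units of the slope itself (.25/.316, about .79 slope SD), it would be 0% to 3% over the same residual range. The protocol states the margin in SD units, so steps 2 and 3 follow its text.

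**The case against.** The strongest reply is that the same paragraph already contains the remedy: a margin-based equivalence test, which is also the only approach with a power statement. That stands. A reader might infer that Hypothesis 2 rests on the constraint alone, or that the plan will declare equality whenever the constraint is non-significant. The documents support neither. The constraint is described as a comparison of relative magnitude, and the phrase "hypothesizing no differences between the Group Based and Web Facilitated conditions" belongs to the second approach. Reporting a difference test beside an equivalence test is ordinary practice.

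Two further limits stand. Calling non-significance at the margin the usual outcome would be too strong: it is 57% at 102 per arm and near one half at 120, and maximum likelihood could let families with partial data contribute, so 102 is not clearly the effective number. Nor should the constraint's behaviour at a difference of .10 SD, where it is non-significant about 89% of the time, be counted as harm. That difference lies inside the margin, which the plan itself treats as equivalent.

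Two replies do not succeed. A rule for disagreement might indeed sit in a statistical analysis plan that is not shown, but the point concerns what the protocol itself fixes: it assigns a test with an equality null to a hypothesis of equality. Second, section 1.1 states power of .98 for effects of .10 in the same growth model, which, if right, would make a non-significant constraint rare at .25 SD. With that section's slope variance and no residual variance at all, power for a contrast of .10 slope SD at 102 per arm is Φ(.0316/.0443 − 1.96) = .106, or .617 if .10 is in raw units. The .98 therefore gives no reassurance here; whether it is right is a separate question.

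**Conclusion.** The point holds as a defect of ranking and interpretation, not as a missing equivalence analysis. Of the two approaches listed for Hypothesis 2, only the margin-based one can support it. With the stated margin and numbers, a non-significant constraint would accompany a true margin-sized difference in about 51% to 57% of trials. This rests on the assumed two-sided .05 level and a simple two-mean approximation. It rises to 65% to 77% with the margin in latent slope SDs and residual variance assumed at .25 to 1.0, and falls to 28% or lower only if the margin is read in raw units, which the text does not say.

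The lack of ranking matters because disagreement is likely on the plan's own inputs: even with no true difference, the second approach succeeds in only about 11% (two one-sided tests) or 56% (one-sided) of trials. That the protocol intends to treat non-significance as support remains an inference, which the text permits but does not state.

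**What to change.** In section 1.1, under the analyses for Hypothesis 2, state three things:

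1. Hypothesis 2 is decided only by the confidence interval for β1 − β2 against the prespecified margin, which is the second approach already planned. A one-sided .05 level corresponds to a two-sided 90% interval.
2. The comparison of constrained and unconstrained models is a supplementary test of difference.
3. A non-significant constraint does not support Hypothesis 2, whatever the result of the margin-based test.

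The first statement also settles what to conclude when the two disagree. The change is wording only and needs no extra families, data or analyses. The downside is the loss of an easier but invalid route to a conclusion of equality. With Hypothesis 2 resting on the margin-based test alone, the stated .82 power should be rechecked, since it does not follow from the inputs given with it.

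### For Hypothesis 2 the protocol plans a one-sided non-inferiority test but sizes a two-sided equivalence test; the planned one cannot support equal effectiveness, and neither has the stated power

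*Protocol*

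**What the plan says.** Protocol section 1.1 states the hypothesis twice. The purpose statement, where it is numbered (1), says "individualized web-facilitated parenting intervention will be equally effective as the group-based web-enhanced intervention". The Analysis of Aim 1, where it becomes Hypothesis 2, says "ADAPT group-based condition will be equally effective as the individualized ADAPT web-facilitated condition".

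The paragraph headed Analyses for Hypothesis 2 of Aim 1 then gives two approaches:

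- First, on the two condition effects in the latent growth model, "we will further specify equality constraints in the LGM model to directly compare the relative magnitude of" those effects.
- Second, "we will conduct a one-sided non-inferiority test (i.e., a test of equivalence) for the intent to treat growth slope factor means and variances".

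The power statement that follows is for an "equivalence test of means using two one-sided tests for two groups of 102 (Group Based and Web Facilitated" arms). It continues: "The study is powered .82 using a .05 one-sided alpha when the reference mean = 1 and the comparison mean = 1", and equal means are still concluded "when the comparison group is plus or minus a quarter of a standard deviation of the reference mean".

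No rule says how the two approaches combine. The paragraph speaks of a reference and a comparison mean without saying which arm is which. Sections 17.1 (Data Analysis Plan) and 17.2 (Power Analysis) do not mention this test, so they do not resolve the matter.

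**The concern.** The protocol treats non-inferiority and equivalence as the same thing. A one-sided non-inferiority test passes whenever the tested arm is shown not to be worse than the reference by more than the margin. It passes just as readily, in fact more readily, when the tested arm is much better. An equivalence test must also rule out a difference in the other direction. The test named for the analysis is therefore neither the one that was sized nor one that can support the hypothesis as worded.

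This hypothesis is one of the trial's two, and Aim 2a separately asks what group delivery adds over the facilitated and self-directed formats. If a real advantage of one format can be reported as equality, the answer to that question is blurred. The choice of test should not be left until results are known, because the two readings can give opposite conclusions on the same data.

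**Working it through.** **Inputs** (Protocol section 1.1): 102 analysed per arm (120 less 15%); one-sided alpha .05; margin .25 SD; true difference 0 for the power statement; stated power .82. Assumed: SD = 1 for the analysed measure, as a margin in SD units implies, and a comparison of two means as an approximation to the slope-factor test.

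Standard error = √(2/102) = .1400 SD. 1.645 × .1400 = .2303.

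**The stated power of .82**

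- One-sided non-inferiority: Φ(.25/.1400 − 1.645) = Φ(.141) = .556 (.554 with the t distribution).
- Two one-sided tests: 2 × .556 − 1 = .112 (.109 with t).

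Neither gives .82. One route comes close: a raw margin of .25 with SD .70, a value the protocol uses for the initial-status factor. That gives Φ(.25/(.70 × .1400) − 1.645) = .817 for a one-sided test. It is then a margin of .25/.70 = .36 SD, not .25 SD, and two one-sided tests with that SD give .63. The protocol does not say whether the figure arose this way.

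**What each rule accepts** (d = observed difference, tested minus reference, in SD)

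- One-sided non-inferiority passes if d > −.25 + .2303 = −.020.
- Two one-sided tests pass if d lies between −.020 and +.020.
- A two-sided .05 test of equality, standing in for the equality constraint, does not reject if |d| < 1.96 × .1400 = .274.

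Suppose d = +.15. The 90% interval is .15 ± .23, or −.08 to .38. Non-inferiority passes, equality is not rejected, and equivalence is not shown.

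**Probability of each result**

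| True advantage of tested arm (SD) | One-sided test passes | Two one-sided tests pass | Equality test rejects | Equality not rejected and one-sided test passes |
|---|---|---|---|---|
| 0 | .556 | .112 | .05 | .53 |
| .25 | .973 | .023 | .43 | .54 |
| .30 | .989 | .011 | .57 | .42 |
| .50 | >.999 | <.001 | .95 | .05 |

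Formulas for true advantage t, with SE = .1400:

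- One-sided: Φ((.25 + t)/SE − 1.645).
- Two one-sided: Φ((.25 − t)/SE − 1.645) + Φ((.25 + t)/SE − 1.645) − 1.
- Equality rejected: Φ(t/SE − 1.96) + Φ(−t/SE − 1.96).
- Last column: Φ((.274 − t)/SE) − Φ((−.020 − t)/SE).

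**What .82 would need at a ±.25 SD margin**

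- Two one-sided tests: 2 × ((1.645 + 1.341)/.25)² gives 286 analysed per arm, or 286/.85 = 337 randomised per arm. With 102 per arm the margin would have to be (1.645 + 1.341) × .1400 = .42 SD.
- One-sided non-inferiority: 2 × ((1.645 + .915)/.25)² gives 210 analysed per arm, or 210/.85 = 248 randomised.

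**The case against.** The best defence is that the paragraph mostly describes equivalence. It glosses the test as one of equivalence, hypothesises no difference, sizes two one-sided tests and gives a symmetric range for concluding equal means. On that reading, one-sided refers to the alpha of each component test, and a clearly better format would not be called equal. The equality-constraint comparison also works in both directions and would usually expose a difference of .50 SD.

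Much of this stands, and it rules out three stronger readings that a reader might infer.

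- *That the one-sided test alone decides Hypothesis 2, so a better format would be declared equal.* The protocol lists two approaches and does not say that either one decides. The false claim of equality is possible under one of two conflicting readings; it is not the settled plan.
- *That the two statements of the hypothesis set opposite test directions.* Equal effectiveness is symmetric, so swapping the arms changes nothing. What is true is narrower: no reference arm is named, and this matters only if a one-sided test is run.
- *That the rule can never fail, because the cut lies just below zero and one direction always passes.* That requires choosing the direction after seeing the data, and nothing in the protocol says this would happen.

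The defence does not remove the contradiction. The planned analysis is called non-inferiority in so many words, and that is not another name for equivalence. Nor does the equality constraint repair it. At .25 SD it rejects less than half the time, and failing to reject equality is not evidence of equality. A reference arm or an interval rule could be left to an SAP, but here the protocol itself names one test and sizes another.

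**Conclusion.** The concern holds as an internal contradiction. The second analysis for Hypothesis 2 is named as one test and sized as another, and the named test cannot support equal effectiveness. If it were run as named, a tested format truly .25 SD better could be declared equal with probability about .97, and one .50 SD better with probability above .999. Under two one-sided tests the figures are about .02 and below .001. The equality constraint would usually catch the larger difference (about .95) but not the smaller (about .43).

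The stated power of .82 fits neither test at the stated margin. These sizes rest on SD = 1, 102 analysed per arm and a two-mean approximation to the growth-model slope test. The exact values would shift under the full model. The difference between what the two tests can establish would not.

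**What to change.** In Analyses for Hypothesis 2 of Aim 1, replace the non-inferiority phrase with the two one-sided tests already used for sizing. Equivalence is supported only if the 90% confidence interval for the Group Based minus Web Facilitated difference in slope means lies wholly within the stated margin. Report the equality-constraint result as supportive, and state that its non-rejection is not taken as evidence of equality.

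If non-inferiority is what is meant, name one reference arm and reword the purpose statement, the Analysis of Aim 1 and the Hypothesis 2 paragraph alike, so that they claim non-inferiority and no longer equal effectiveness.

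In either case restate the power for the test chosen. The text change is small but the consequence is not: with the stated inputs, power is about .11 for two one-sided tests and about .56 for one-sided non-inferiority. An inconclusive result on Hypothesis 2 then becomes likely, and the protocol should say so. Recovering .82 for equivalence at ±.25 SD would take about 337 randomised families per arm against the planned 120. Keeping the planned size would need a margin near ±.42 SD, which would have to be justified on its own merits.
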